8.4 Prior and concomitant therapies

All medications and treatments (i.e., prescription drugs [including COVID-19 vaccination programs, see [Table 3](#)], over the counter [OTC] drugs and vitamins, herbal and dietary supplements, and lubricants used with sex), hereafter referred to as therapies, taken within 30 days prior to screening will be recorded as prior therapies at the Screening 1 visit.

All therapies used after the screening 1 visit will be recorded as concomitant therapies.

Information about the total daily dose, route of administration, start and discontinuation dates, and indication are to be recorded in the eCRF.

8.5 Efficacy assessments

8.5.1 Clinician reported outcomes (ClinRO) assessments

8.5.1.1 Imaging of VLS

Imaging of the vulvar region (i.e., clitoris and periclitoral skin, interlabial sulci, labia minora, posterior fourchette and perineum, anal and perianal skin), must be obtained by the investigator (preferably the same investigator at all visits for a specific patient) at Screening 1, Baseline, Week 1, Week 4, Week 8 and Week 12 (or Early Termination) for all patients. Imaging of VLS should preferably be performed BEFORE the scoring of the VASSI.

Detailed description of the imaging procedure will be provided in a separate imaging manual. Steps will be taken to ensure that the images are pseudonymised.

8.5.1.2 Vulvar lichen sclerosus Area and Sign Severity Index (VASSI)

The Vulvar lichen sclerosus Area and Sign Severity Index (VASSI) evaluates the severity of 3 non-permanent signs of VLS in 5 different vulvar areas. It must be performed by the investigator (preferably the same investigator at all visits for a specific patient) at Screening 1, Baseline, Week 1, Week 4, Week 8 and Week 12 (or Early Termination) for all patients. It should preferably be performed AFTER Imaging of VLS and BEFORE scoring of the CGA.

Areas: The 5 different vulvar areas are Clitoris and periclitoral skin (**C**), Right interlabial sulcus and labium minus (**R**), Left interlabial sulcus and labium minus (**L**), Posterior fourchette and perineum (**P**), Anus and perianal skin (**A**)), see [Figure 2](#).

Signs: The 3 non-permanent signs of VLS are **Fissures/erosions** (longitudinal/patchy ruptures of the skin surface), **Ecchymoses** (bleedings within the skin) and **Hyperkeratoses** (patches/plaques of bright white skin with a ‘powdery’ texture). **IMPORTANT**: Hyperkeratoses must be distinguished from Sclerosis (areas of yellowish/ivory white skin with a smooth/waxy/firm texture) and Pallor (areas of pale whitish skin that differ from hyperkeratosis in that they are not “powdery”). Sclerosis and pallor are permanent signs of VLS.

Severity: The severity must be scored on a 4-point scale from 0-3 (i.e., 0 (no lesion), 1 (length of lesion \leq 5 mm), 2 (length of lesion $>$ 5mm and \leq 10 mm) or 3 (length of lesion $>$ 10 mm)) for each non-permanent sign in each vulvar area (i.e., the light grey cells in [Table 4](#)). Note: The measure included in the photocard used for imaging of VLS must be used as reference when assigning severity scores. In case a non-permanent sign extends from one vulvar area into another, then it must be scored in both areas according to the length of the lesion in the particular area. In contrast, if a non-permanent sign involves the border between two areas, it should only be scored for the area that is most involved/affected to avoid scoring the same lesion twice.

A scoring manual will be available.

For endpoint analyses, the VASSI Area scores, VASSI Sign scores and Total VASSI score (i.e., the white cells in [Table 4](#)) will be calculated as follows:

1. A VASSI Area score (**VASSI_C, -R, -L, -P, -A**) is calculated by summing up the 3 severity scores for Fissures/erosions, Ecchymoses and Hyperkeratoses in the particular vulvar area [range 0-9].
2. A VASSI Sign score (**VASSI_F, -E, -H**) is calculated by summing up the severity scores for a particular sign across all 5 vulvar areas [range 0-15]
3. The Total VASSI (**VASSI**) score is calculated by summing the 5 VASSI Area scores or VASSI Sign scores [range 0-45]

[figure not shown]
Table 4: Vulvar lichen sclerosus Area and Sign Severity Index (VASSI)

Vulvar areas Signs	Clitoris and periclitoral skin (C)	Right interlabial sulcus and labium minus (R)	Left interlabial sulcus and labium minus (L)	Posterior fourchette and perineum (P)	Anus and perianal skin (A)	VASSI Sign scores
Fissures / erosions (F)						VASSI _F =
Ecchymoses (E)						VASSI _E =
Hyperkeratoses (H)*						VASSI _H =
VASSI Area scores	VASSI _C =	VASSI _R =	VASSI _L =	VASSI _P =	VASSI _A =	Total VASSI score =

Light grey cells must be filled in by the investigator with severity scores. The severity must be scored on a 4-point scale (i.e., 0 (no lesion), 1 (length of lesion \leq 5 mm), 2 (length of lesion $>$ 5mm and \leq 10 mm) or 3 (length of lesion $>$ 10 mm) for each non-permanent sign in each vulvar area; White cells will be calculated.

*IMPORTANT: Hyperkeratoses (patches/plaques of bright white skin with a ‘powdery’ texture) is a non-permanent sign of VLS and must be distinguished from Sclerosis (areas of yellowish/ivory white skin with a smooth/waxy/firm texture) and Pallor (areas of pale whitish skin that differ from hyperkeratosis in that they are not “powdery”). Sclerosis and pallor are permanent signs of VLS.

Figure 2: Vulvar areas

8.5.1.3 Clinician's Global Assessment (CGA) of VLS

The Clinician's Global Assessment (CGA) of VLS evaluates the global (overall) severity of VLS in the entire vulvar region (i.e., including the clitoris, periclitoral skin, interlabial sulci, labia minora, posterior fourchette and perineum, anal and perianal areas). It should preferably be performed AFTER the scoring of the VASSI and BEFORE scoring of the CGIC.

The CGA must be evaluated by the investigator (preferably the same investigator at all visits for a specific patient) on a 5-point scale ranging from Clear to Severe at Screening 1, Baseline, Week 1, Week 4, Week 8, and Week 12 or Early Termination using [Table 5](#) below :

Table 5: Clinician's Global Assessment (CGA) of VLS

CGA score	Description

Clear	No visible Non-permanent signs* of VLS (Fissures/Erosions, Ecchymoses or Hyperkeratoses) in the vulvar region. Note: Permanent signs [#] of VLS may be present
Almost clear	Barely visible Non-permanent signs* of VLS (Fissures/Erosions, Ecchymoses or Hyperkeratoses) in the vulvar region.
Mild	Slightly visible Non-permanent signs* of VLS (Fissures/Erosions, Ecchymoses or Hyperkeratoses) in the vulvar region.
Moderate	Easily visible Non-permanent signs* of VLS (Fissures/Erosions, Ecchymoses or Hyperkeratoses) in the vulvar region.
Severe	Markedly visible Non-permanent signs* of VLS (Fissures/Erosions, Ecchymoses or Hyperkeratoses) in the vulvar region.

*Non-permanent signs of VLS include fissures/erosions (longitudinal/ respectively patchy ruptures of the skin surface), ecchymoses (bleedings inside the skin) and hyperkeratoses (patches/plaques of bright white skin with a ‘powdery’ texture). Hyperkeratoses must be distinguished from Sclerosis (areas of yellowish/ivory white skin with a smooth/waxy/firm texture) and pallor (areas of pale whitish skin that differ from hyperkeratosis in that they are not ‘powdery’)

[#] Permanent signs of VLS include e.g., atrophy, sclerosis, pallor, scarring or fusion.

A scoring manual will be available.

8.5.1.4 Clinician's Global Impression of Change (CGIC) of VLS

Clinician's Global Impression of Change (CGIC) in non-permanent signs of VLS including fissures/erosions (longitudinal/respectively patchy ruptures of the skin surface), ecchymoses (bleedings inside the skin) and hyperkeratoses (patches/plaques of bright white skin with a ‘powdery’ texture) must be assessed by the investigator (preferably the same investigator at all visits for a specific patient) at Week 1, Week 4, Week 8, and Week 12 or Early Termination visits using the below 7-item verbal rating scale. It should preferably be performed AFTER the scoring of the CGA:

Please choose the response below that best describes the overall change in the patient's non-permanent signs of vulvar lichen sclerosus since the trial medication was started at baseline, based on the baseline image of VLS (see Section 8.5.1.1 ‘Imaging of VLS’):

- Very much better
- Much better
- A little better
- No change
- A little worse
- Much worse
- Very much worse

8.5.2 Patient reported outcomes (PRO) assessments

8.5.2.1 Worst Itch Numeric Rating Score (WI-NRS) of VLS

The patient's WI-NRS score must be recorded by the patient in a diary once daily (i.e., every day around the same timepoint, e.g. morning, afternoon or evening) for a total of 7 days (i.e. starting 7 days before the next in-clinic visit and ending on the day before the next in-clinic visit) leading up to each in-clinic visit day at Baseline, Week 1, Week 4, Week 8, and Week 12 (or Early Termination) using an 11-point numeric rating scale ranging from 0 to 10:

Please score the intensity of the Worst Itch associated with your lichen sclerosus, that you have experienced in the past 24 hours: 0 (no itch), 1, 2, 3, 4, 5, 6, 7, 8, 9, 10 (worst imaginable itch).

In addition, the patient's WI-NRS score must be reported to the clinical staff at in-clinic visits at Screening 1, Baseline, Week 1, Week 4, Week 8, and Week 12 or Early Termination using the 11-point numeric rating scale above.

8.5.2.2 Worst Pain Numeric Rating Score (WP-NRS) of VLS

The patient's WP-NRS score must be recorded by the patient in a diary once daily (i.e., every day around the same timepoint, e.g. morning, afternoon or evening) for a total of 7 days (i.e. starting 7 days before the next in-clinic visit and ending on the day before the next in-clinic visit) leading up to each in-clinic visit day at Baseline, Week 1, Week 4, Week 8, and Week 12 (or Early Termination) using an 11-point numeric rating scale ranging from 0 to 10:

Please score the intensity of the Worst Pain* associated with your lichen sclerosus, that you have experienced in the past 24 hours: 0 (no pain), 1, 2, 3, 4, 5, 6, 7, 8, 9, 10 (worst imaginable pain).

*Pain includes sensations such as Burning, Stinging, Soreness and Irritation.

In addition, the patient's WP-NRS score must be reported to the clinical staff at in-clinic visits at Screening 1, Baseline, Week 1, Week 4, Week 8, and Week 12 or Early Termination using the 11-point numeric rating scale above.

8.5.2.3 Worst Penetrative sex related Pain Numeric Rating Score (WPP-NRS) of VLS

At Screening 1, Baseline, Week 4, Week 8, and Week 12 or Early Termination visit all patients must indicate whether they are sexually active or not by answering Question 1 below. Patients who answer No to Question 1, must subsequently answer only Question 2. Patients who answer Yes to Question 1 must subsequently answer Questions 2, 3, and 4, and finally in Question 5 report their Worst Penetrative sex related Pain on an 11-point numeric rating scale ranging from 0 to 10 as also described below:

1. Have you had penetrative sex during the past 4 weeks? (Yes/No)
If No, please answer Question 2 only. If Yes, please answer Questions 2, 3, 4 and 5.
2. Have you abstained from penetrative sex during the past 4 weeks due to your vulvar lichen sclerosus? (Yes/No)

3. How many times have you had penetrative sex during the past 4 weeks? (X times)
4. Have you used lubricants during penetrative sex during the past 4 weeks? (Yes/No)
5. Please score the intensity of the Worst Penetrative sex related Pain* you have experienced due to your lichen sclerosus in the past 4 weeks: 0 (no penetrative sex related pain), 1, 2, 3, 4, 5, 6, 7, 8, 9, 10 (worst imaginable penetrative sex related pain).

*Pain includes sensations such as Burning, Stinging, Soreness and Irritation.

8.5.2.4 Patient's Global Impression of Change (PGIC) of VLS

PGIC in Worst Itch (WI), Worst Pain (WP) and Worst Penetrative sex related Pain (WPP) must be reported to the clinical staff at Week 4, Week 8, and Week 12 or Early Termination visits using a 7-item verbal rating scale:

Please choose the response below that best describes the overall change in your [Worst Itch*] associated with your lichen sclerosus since you started applying the trial medication:

- Very much better
- Much better
- A little better
- No change
- A little worse
- Much worse
- Very much worse

*Repeat with Worst Pain and Worst Penetrative sex related Pain.

8.5.2.5 Patient's rating of importance of improvements of VLS

Patients reporting an improvement in PGIC (i.e., 'Very much better', 'Much better' or 'A little better') must report the Importance of the improvement to the clinical staff at Week 4, Week 8, and Week 12 or Early Termination visits using a 2-item Importance Questionnaire:

Question 1: You have reported an improvement in your [Worst Itch*] associated with your lichen sclerosus since you started applying the trial medication. Was the improvement important to you? (Yes/No). If yes, please proceed to question 2.

Question 2: In which way(s) was the improvement in your [Worst Itch*] associated with your lichen sclerosus important to you? (*Free text*).

*Repeat with Worst Pain and Worst Penetrative sex related Pain.

8.5.2.6 International Consultation on Incontinence Questionnaire Urinary Incontinence Short Form (ICIQ-UI-SF)

Incontinence status must be evaluated by the patient at Baseline and Week 12 or Early termination visits using the ICIQ-UI-SF questionnaire.

The ICIQ-UI-SF is a validated questionnaire with a recall period of 4 weeks comprising a total of 4 questions about when, how often and how much urine is leaked and how much urine leaking interferes with everyday life. The ICIQ-UI-SF score ranges from a maximum score of 21 (indicating maximum burden) and a minimum score of 0 (indicating no burden). A score ≥ 1 indicates urinary incontinence ([Avery et al., 2004](#)).

8.5.2.7 Menopausal status and Menstrual cycle status

Menopausal status (Pre-menopausal or Menopausal) in accordance with inclusion criterion 9, Section [5.2](#) must be recorded for all women at Baseline and Week 12 (or Early Termination) visits.

Menstrual cycle status (i.e., whether the patient is menstruating or not, reason in case of no menstruation, number of days since the first day of the latest menstruation period, average duration of menstruation period in days, regularity of menstrual cycle) must be evaluated by all pre-menopausal women at Baseline, and Week 12 (or Early Termination) visits.

8.5.2.8 Skindex-29

Skindex-29 is a skin specific multidimensional quality-of-life instrument. It must be evaluated by the patient at Baseline, Week 4, Week 8, and Week 12 or Early Termination visits using the Skindex-29 Quality of Life Index questionnaire. It inquires how often (1. Never, 2. Rarely, 3. Sometimes, 4. Often, 5. All the time) during the previous 4 weeks the patient experienced the effect described in each item. Seven items address the Symptoms domain, ten items the Emotional domain, and twelve items the Functioning domain. All responses are transformed to a linear scale of 100, varying from 0 (no effect) to 100 (effect experienced all the time). Skindex-29 scores are reported as three scale scores, corresponding to the three domains; a scale score is the average of a patient's responses to items in a given domain ([Chren et al., 1997](#)).

8.5.2.9 VQLI

The Vulvar Quality of Life Index (VQLI) questionnaire is a vulvar specific quality-of-life instrument which was validated in cohorts of women including 40-50% Lichen Sclerosus patients. It must be evaluated by the patient at Baseline, Week 4, Week 8, and Week 12 or Early Termination visits using the Vulvar Quality of Life Index (VQLI) questionnaire. In the context of this trial, the vulvar region includes clitoris and periclitoral skin, interlabial sulci, labia minora, posterior fourchette and perineum, anal and perianal skin.

The questionnaire comprises a total of 15 questions with a recall period of 1 month under the following domains: Symptoms (Questions 1–2); Feelings and Emotions (Questions 3–5); Activities of daily living (Questions 6–10); Relationships (Question 11); Sexual function (Questions 12–13);

Future health concerns (Question 14); and Treatment (Question 15). Each of the questions are graded zero to three on a Likert scale, with 0 representing no symptom or complaint ('Not at all' or 'Not applicable'), 1 ('A little'), 2 ('A lot') and 3 ('Very much'), resulting in a maximum score of 45/45 and a minimum score of 0/45 ([Saunderson et al., 2020](#)).

8.5.2.10 VLS patient journey sheet

The Burden of living with VLS before entering the trial must be described by the patient by filling in the 'VLS patient journey sheet' at the Screening 1 visit. The patient journey sheet is a questionnaire which collects information about:

- which issues the VLS patient has experienced in relation to VLS
- which issues experienced in relation to VLS the patient has found most burdensome.

8.6 Safety and other assessments

8.6.1 Physical examination

A complete (i.e., including all organ systems as well as the vulvar region) physical examination is required at Screening 1 and Week 12 (EoT or Early Termination) visits.

An abbreviated physical examination (including the vulvar region as minimum; other organ systems may be included depending on present signs, symptoms, or investigation outcomes) is required at the Baseline visit (and if judged necessary by the investigator) at the FU visit.

Any abnormalities must be assessed as "clinically significant" or "not clinically significant" by the investigator. Abnormalities classified as "clinically significant" must be recorded in the eCRF as AEs.

8.6.2 Vital signs

Vital signs (Systolic Blood Pressure, Diastolic Blood Pressure, Heart rate and Temperature) will be recorded by trained clinical staff at Baseline and Week 12 (or Early termination) visits. Vital signs are also recorded at Week 14 (Follow-up) if judged necessary by the investigator.

Any abnormalities must be assessed as "clinically significant" or "not clinically significant" by the investigator. Abnormalities classified as "clinically significant" must be recorded in the eCRF as AEs.

8.6.3 Urine pregnancy test

A highly sensitive urine pregnancy test (i.e., with a sensitivity down to at least 25 mIU/ml for human chorionic gonadotrophin (hCG) will be collected from women of childbearing potential (see inclusion criterion 9, Section 5.1) by trained clinical staff at all in-clinic visits and must be recorded in the eCRF. Urine pregnancy test samples will be destroyed after the results of the test have been recorded.

If there is suspicion of pregnancy at any time during the trial, an additional urine sample will be obtained and analysed. Should a participant become pregnant during the trial, treatment must be discontinued, and the patient must be withdrawn from the trial.

All pregnancies (occurring before or after start of IMP administration) should be immediately reported to MC2 or designee and followed through to resolution (i.e., delivery, miscarriage, or elective abortion). The report should be submitted within the same timelines as an SAE (within 24 hours of knowledge), although a pregnancy per se is not considered an SAE.

8.7 Laboratory assessments

8.7.1 Analysis of laboratory samples

There will be no scheduled sampling for clinical laboratory analyses in this trial.

If there is a suspicion of a medical condition (considered related or not to the IMP), relevant laboratory samples may be taken and analysed at the discretion of the investigator. No samples will be stored for future analysis.

8.8 Adverse events and serious adverse events

8.8.1 Definition of adverse events (AE)

An AE is any untoward medical occurrence in a patient or clinical investigation participant administered an investigational or non-investigational medicinal product and which does not necessarily have to have a causal relationship with this treatment. An AE can therefore be any unfavourable and unintended sign, symptom, or disease temporally associated with the use of a medicinal product, whether considered related to the medicinal product or not. Such unfavourable signs, symptoms or diseases may be discovered via any trial assessment (e.g., laboratory findings, PRO questionnaires, physical examination).

8.8.2 Definition of serious adverse events (SAE)

An SAE is any untoward medical occurrence that at any dose:

- Results in death
- Is life-threatening
- Requires in-patient hospitalisation or prolongation of existing hospitalisation

- Results in persistent or significant disability/incapacity
- Is a congenital anomaly/birth defect
- Other serious or important medical event

Any important medical events that may not result in death, be life-threatening, or require hospitalisation may be considered an SAE when, based on appropriate medical judgment, they may jeopardise the participant or the participant may require medical or surgical intervention to prevent one of the outcomes listed in the above definitions.

The death of a participant enrolled in a trial is per se not an event, but an outcome. Any event resulting in a fatal outcome must be fully documented and reported, regardless of the causality relationship to the IMP.

Any pre-planned hospitalisations or procedures that are known at the time of signing the informed consent form will not be recorded as SAEs but will be recorded as AEs only.

All SAEs will be assessed for expectedness by the sponsor or designee. An SAE is considered “unexpected” if its nature or severity is not included in the IB, Section 6.2.12.

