8.8.4 Time period and frequency for event assessment and follow-up

8.8.4.1 Adverse event reporting

The investigator or designee (as per site delegation log) is responsible for obtaining, assessing, and documenting all AEs during the trial.

Adverse event information will be collected from individual trial patients from signature of the informed consent form until the last trial visit.

All AEs will be documented in the eCRF, including a description of each AE, AE relationship to IMP, start and stop dates, seriousness, severity, action taken (with the IMP and other actions taken) and outcome.

If the event is reported as an SAE, the timelines for SAE reporting apply (see Section [8.8.4.2](#)). If the event is reported as non-serious AE, it should be reported on the appropriate eCRF page.

Throughout the trial, the occurrence of AEs should be monitored by nondirective questioning of the patient at each visit. Information on AEs can also be obtained from signs and symptoms detected during examinations, observations made by the site staff, or spontaneous reports from patients. Pre-existing conditions that worsen during the trial should also be recorded as AEs. This will also include worsening of the disease as judged by the investigator.

AEs requiring therapy must be treated in accordance with recognised standards of medical care to protect the health and well-being of the patient. Treatment due to an AE will be recorded in the patient's records and on the appropriate eCRF.

All SAEs and related non-serious AEs must be followed by the investigator until they are resolved or until judged by the investigator to be stable/need no further follow-up. Unrelated non-serious AEs must be followed by the investigator until the patient's last trial visit. All relevant follow-up information will be reported in the eCRF (and to PharmaLex if it qualifies as an SAE, see Section 8.8.9.1).

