9.4.3.2 Adverse events

Adverse events will be coded using Medical Dictionary for Regulatory Activities (MedDRA) terminology. Treatment-emergent adverse events (TEAEs), related TEAEs, non-serious TEAEs, serious TEAEs, related serious TEAEs, TEAEs leading to treatment discontinuation and deaths will be summarised by the overall incidence of at least one event, incidence by body system, and incidence by body system and preferred term. Each patient will contribute only once (e.g., the first occurrence) to each of the rates, regardless of the number of occurrences (events) the patient experiences. The number of occurrences will also be displayed.

Treatment-emergent AEs will be summarised by severity (mild, moderate, or severe), and by relationship to trial product (not related, unlikely, possibly, or probably). In summaries of severity and relationship, patients who report more than one event that are mapped to the same preferred term will be counted only once under the strongest severity and last relationship, accordingly. An AE is treatment-emergent if its date of onset is on or after the day of start of trial medication. An AE is related if relationship to trial product is not assessed as unrelated.

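### Protocol 8.8.2 has hospitalisations and procedures planned before consent recorded as AEs, which conflicts with 8.8.1 and can put events that are not untoward into the TEAE tables

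*Protocol*

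**What the plan says.** Protocol 8.8.2 sets a rule for "Any pre-planned hospitalisations or procedures that are known at the time of signing the informed consent form": these "will not be recorded as SAEs but will be recorded as AEs only". The rule does not require that the event be untoward. It also does not mention what happens if a planned stay is prolonged or a complication occurs.

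Four other provisions bear on it:

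- **AE definition, protocol 8.8.1:** "An AE is any untoward medical occurrence in a patient".
- **Pre-existing disease, protocol 8.8.4.1:** "Pre-existing conditions that worsen during the trial should also be recorded as AEs". AEs are collected "from signature of the informed consent form until the last trial visit".
- **Seriousness, protocol 8.8.2:** one of the listed criteria is "Requires in-patient hospitalisation or prolongation of existing hospitalisation". The SAP repeats it among the SAE criteria in section 2.4.2.
- **Treatment emergence:** protocol 9.4.3.2 states "An AE is treatment-emergent if its date of onset is on or after the day of start of trial medication". SAP 4.4.5 is narrower. The event must start on or after the first day of IMP and have been absent before treatment, or have been present and become more severe.

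The SAP has no rule on planned hospitalisations or procedures. Its list of AE attributes in section 2.4.2 has no field that marks an event as planned before consent.

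**The concern.** An operation booked before consent for a condition that has not changed is intended, and nothing has worsened. It meets neither the definition in 8.8.1 nor the worsening rule in 8.8.4.1, yet 8.8.2 has it recorded as an AE. The protocol therefore creates records that are not AEs by its own definition, and the SAP passes them on to the tables without a filter.

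Exploring safety is a secondary objective, and the frequency of treatment-emergent AEs is the first endpoint listed for it in protocol section 3. There are no scheduled safety laboratory samples (8.7.1) and no data safety monitoring board (10.1.7), so the AE tables carry most of the safety evidence. With 16 to 17 women per arm (9.2), one record is visible in a percentage. Such a record also needs a severity grade. Protocol 8.8.3.1 calls an event severe when the patient cannot carry out her usual activities, so an uneventful elective operation could appear as a severe event in the maximum-severity table.

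A second, smaller matter is silence. A site reading 8.8.2 is not told how to report a complication or a prolonged stay that follows a planned admission.

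**Working it through.** The plan states no figure for planned procedures, so there is nothing to reproduce. The check compares the definitions and then works out the weight of one patient.

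**Step 1. Is a planned procedure an AE?** By 8.8.1 it is not, unless something untoward happened. By 8.8.4.1 it is not, unless the underlying condition worsened. By 8.8.2 it is recorded as one regardless. The sections disagree.

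**Step 2. Can it become a TEAE?** This depends on timing and on the term recorded.

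| Recorded term and timing | Protocol 9.4.3.2 | SAP 4.4.5 |
|---|---|---|
| Procedure, between consent and first application | Not a TEAE | Not a TEAE |
| Procedure, on or after first application | TEAE (by onset date) | TEAE (procedure absent before treatment) |
| Underlying condition, present earlier and unchanged, with its true onset date | Not a TEAE | Not a TEAE |

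Only the second row puts a planned event into the counts. The documents do not say whether sites record the procedure or the condition, so the supported statement is that a planned event *can* enter the counts.

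**Step 3. Does anything remove it later?** The AE tables in SAP 5.5.4 and section 7.3 take all treatment-emergent events. No exclusion for planned events is written there or in SAP 2.4.2.

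**Step 4. What does one record weigh?** Inputs: 16 to 17 patients per arm and 33 in total (protocol 9.2). For a woman with no other TEAE, the shift in incidence is 1/n:

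- arm of 17: 1/17 = 5.9 percentage points
- arm of 16: 1/16 = 6.3 percentage points
- both arms together: 1/33 = 3.0 percentage points

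If she has another TEAE, the overall incidence does not move. Only the event count and the rows for that organ class and preferred term change.

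**Step 5. Is the shift related to treatment?** The event was fixed before consent, hence before randomisation, and the trial is double-blind. Allocation is independent of it, so in expectation it falls equally on both arms.

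**Step 6. How does 8.8.2 treat a prolonged planned stay?** The exemption covers what was planned and known at consent. An unplanned prolongation was neither. Prolongation is a seriousness criterion in the same section, and 8.8.4.2 sends every SAE to the 24-hour route. The provisions can be followed together, but none says expressly that such a case remains reportable as an SAE.

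**The case against.** The case for leaving the text alone has real weight. Over-recording is the cautious direction for safety data. Safety analyses are descriptive and exploratory (SAP 5.5.5), with no test between arms. A record assessed as not related stays out of the drug-related tables, and every AE is listed individually, so a reader can recognise an elective procedure. Protocol 2.3.3 also expects exclusion criterion 6 to keep out elderly women with significant comorbidities, which makes planned procedures less likely. All of this stands, and it limits the consequence. It does not remove the contradiction between 8.8.1 and 8.8.2, or the missing filter.

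A reader might make two stronger inferences that the documents do not support.

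- **That a prolonged planned stay is barred from SAE status.** Step 6 shows that it is not. The text only lacks an explicit statement.
- **That an arm's incidence could be far off.** Three such women in one arm would give 3/17 = 17.6 to 3/16 = 18.8 points. No document gives a count of three, or any count. The figure also needs all three procedures after the first application and no other TEAE in any of the women. With a 17:16 split, three given women fall in the same arm with probability (680 + 560)/5456 = 23%, before those conditions apply.

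**Conclusion.** The point holds in a limited form. Protocol 8.8.2 requires AE recording of planned events that need not be untoward, contrary to 8.8.1. Where the procedure is the recorded term and it takes place on or after the first application, it can count as a TEAE, and nothing takes it out again.

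The size is 5.9 to 6.3 percentage points of one arm's incidence for each such woman, provided she has no other TEAE. The total cannot be calculated because the number of such women is not given, and it is zero if there are none. The effect is noise unrelated to arm, not systematic bias. On SAE reporting, the defect is a missing clarification that could lead a site to under-report. The text does not prohibit such a report.

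**What to change.** **Protocol 8.8.2.** Replace the sentence with wording to this effect:

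> A hospitalisation or procedure planned before consent is not in itself an AE. The underlying condition is recorded in the medical history and the procedure under concomitant therapies. Any worsening, complication or prolongation is recorded as an AE or SAE by the usual criteria.

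The destinations exist: SAP 2.5.3 covers medical and surgical history, and SAP 2.4.4 classifies therapies and procedures by timing.

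**SAP.** Recruitment stopped at 33 (SAP 2.1), so the protocol sentence alone may change little in what has been recorded. Add a rule to SAP 5.5.4, and note it in 5.6: records consisting only of an event planned before consent are identified at the blinded database review already scheduled in SAP 3.5, listed separately, and left out of the TEAE summaries. A complication, worsening or prolongation stays in. If it cannot be established that the event was planned before consent, the record stays in as well. The rule must be fixed before unblinding.

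**Cost.** One protocol sentence, one SAP rule and one extra listing. The downside is a small manual review, because the AE attributes include no flag for planned events. With 33 women this is modest.
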